- If after start of IV methylprednisolone at 2 to 4 mg/kg/day there is no improvement within 3 to 5 days, consider start of immunosuppressive therapy such as TNF inhibitors (e.g., infliximab at 5 mg/kg every 2 weeks). Caution: It is important to rule out sepsis and refer to infliximab label for general guidance before using infliximab.
- Consider whether patient may require IV IG, plasmapheresis.
- Once the patient is improving, gradually taper steroids over ≥ 28 days and consider prophylactic antibiotics, antifungals, or anti-PJP treatment (refer to current NCCN guidelines for

Additional Information:

- ❖ If drugs are given and then patient develops AE before or during radiation, radiation is also held, stopped, unless the treatment field is clearly unrelated to the AE (e.g. liver radiation in a patient who develops pneumonitis), provided the patient is clinically stable for radiation treatment.
- ❖ If either drugs are held then radiation is also held. If all radiation has not been delivered as per protocol, radiation would resume the week following the next drug administration, do not skip.
- ❖ If drugs are held, then any remaining radiation is also held until a week after the next cycle begins, per protocol.
- ❖ If patient experiences an AE, requiring drug hold/discontinuation, both drugs will be held.
- ❖ If drug or radiation is permanently discontinued for toxicity before completion of protocol treatment, the subject would need to come off treatment.

Infusion-Related Reactions		Dose Modifications	Toxicity Management
Severity Grade Any Grade			
 - Management per institutional standard at the discretion of investigator - Monitor patients for signs and symptoms of infusion-related reactions (e.g., fever and/or shaking chills, flushing and/or itching, alterations in heart rate and blood pressure, dyspnea or chest discomfort, skin rashes etc.) and anaphylaxis (e.g., generalized urticaria, angioedema, wheezing, hypotension, tachycardia, etc.)
Grade 1	The infusion rate of study drug/study regimen may be decreased by 50% or temporarily interrupted until resolution of the event		For Grade 1 or Grade 2: 
 - Acetaminophen and/or antihistamines may be administered per institutional standard at the discretion of the investigator - Consider premedication per institutional standard prior to subsequent doses - Steroids should not be used for routine premedication of Grade ≤ 2 infusion reactions.
Grade 2	The infusion rate of study drug/study regimen may be decreased 50% or temporarily interrupted until resolution of the event Subsequent infusions may be given at 50% of the initial infusion rate		
Grade 3/4	Permanently discontinue study drug/study regimen		For Grade 3 or 4: Manage severe infusion-related reactions per institutional standards (e.g., IM epinephrine, followed by IV diphenhydramine and ranitidine, and IV glucocorticoid)

Non-immune Mediated Reactions (Note: As applicable, for early phase studies, the following sentence may be added: "Any event greater than or equal to Grade 2, please discuss with Study Physician")		
CTC Grade/Severity	Dose Modification	Toxicity Management
Any Grade	Note: dose modifications are not required for adverse events not deemed to be related to study treatment (i.e. events due to underlying disease) or for laboratory abnormalities not deemed to be clinically significant.	Treat accordingly as per institutional standard
1	No dose modifications	Treat accordingly as per institutional standard

Non-immune Mediated Reactions		
(Note: As applicable, for early phase studies, the following sentence may be added: “Any event greater than or equal to Grade 2, please discuss with Study Physician”)		
CTC Grade/Severity	Dose Modification	Toxicity Management
2	Hold study drug/study regimen until resolution to ≤ Grade 1 or baseline	Treat accordingly as per institutional standard
3	Hold study drug/study regimen until resolution to ≤ Grade 1 or baseline For AEs that downgrade to ≤ Grade 2 within 7 days or resolve to ≤ Grade 1 or baseline within 14 days, resume study drug/study regimen administration. Otherwise, discontinue study drug/study regimen	Treat accordingly as per institutional standard
4	Discontinue Study drug/study regimen (Note for Grade 4 labs, decision to discontinue should be based on accompanying clinical signs/symptoms, Investigator’s clinical judgment and in consultation with the sponsor)	Treat accordingly as per institutional standard

Abbreviations:

AChE = acetylcholine esterase; ADA = American Dietetic Association; AE = adverse event; ALP = alkaline phosphatase; ALT = alanine aminotransferase; AST = aspartate aminotransferase; CT = computed tomography; GI = gastrointestinal; IDS=Infectious Disease Service; ILD = interstitial lung disease; IM = intramuscular; irAE = immune-related adverse event; IV = intravenous; NCI CTCAE = National Cancer Institute Common Terminology Criteria for Adverse Events; PO = by mouth; TNF = tumor necrosis factor; TSH = thyroid stimulating hormone; ULN = upper limit of normal.

ⁱ ASCO Educational Book 2015 “Managing Immune Checkpoint Blocking Antibody Side Effects” by Michael Postow MD

ⁱⁱ NCI CTCAE version 5.0

ⁱⁱⁱ ASCO Educational Book 2015 “Managing Immune Checkpoint Blocking Antibody Side Effects” by Michael Postow MD

^{iv} FDA Liver Guidance Document 2009 Guidance for Industry: Drug Induced Liver Injury – Premarketing Clinical Evaluation

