- Any Grade 3 or 4 noninfectious pneumonitis irrespective of duration
- Any Grade 2 pneumonitis that does not resolve to \leq Grade 1 within 3 days of the initiation of maximal supportive care
- Any Grade 3 irAE, excluding colitis or pneumonitis, that does not downgrade to Grade 2 within 3 days after onset of the event despite optimal medical management including systemic corticosteroids or does not downgrade to \leq Grade 1 or baseline within 14 days
- Liver transaminase elevation $> 8 \times$ ULN or total bilirubin $> 5 \times$ ULN
- Any grade 3 or 4 febrile neutropenia
- Any grade 3 or 4 thrombocytopenia with significant bleeding
- Any \geq Grade 3 non-irAE, except for the exclusions listed below

The definition excludes the following conditions:

- Grade 3 fatigue lasting ≤ 7 days
- Grade 3 endocrine disorder (thyroid, pituitary, and/or adrenal insufficiency) that is managed with or without systemic corticosteroid therapy and/or hormone replacement therapy and the subject is asymptomatic
- Grade 3 inflammatory reaction attributed to a local antitumor response (eg, inflammatory reaction at sites of metastatic disease, lymph nodes, etc)
- Concurrent vitiligo or alopecia of any AE grade

- Grade 3 infusion-related reaction (first occurrence and in the absence of steroid prophylaxis) that resolves within 6 hours with appropriate clinical management
- Grade 3 or 4 neutropenia that is not associated with fever or systemic infection that improves by at least 1 grade within 3 days. Grade 3 or Grade 4 febrile neutropenia will be a DLT regardless of duration or reversibility
- Grade 3 or 4 lymphopenia
- Grade 3 thrombocytopenia that is not associated with clinically significant bleeding that requires medical intervention, and improves by at least 1 grade within 3 days
- Isolated Grade 3 electrolyte abnormalities that are not associated with clinical signs or symptoms and are reversed with appropriate maximal medical intervention within 3 days
- Grade 3 fever lasting \leq 24 hours with or without medical therapy and is not considered an SAE

Immune-related AEs (irAEs) are defined as AEs of immune nature (i.e., inflammatory) in the absence of a clear alternative etiology. In the absence of clinical abnormality, repeat laboratory testing will be conducted to confirm significant laboratory findings prior to designation as a DLT.

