
PLEASE SEE shaded area immediately below this section to find guidance for management of "Hepatitis (elevated LFTs)" in HCC patients
	
Grade 2 (Based on ULN regardless of baseline LFT)AST or ALT >3.0×ULN and $\leq 5.0 \times$ULN and/or TB >1.5×ULN and $\leq 3.0 \times$ULN)
	
Hold Study drug/study regimen dose until grade 2 resolution to \leq Grade 1
 
 • If toxicity worsens then treat as Grade 3 or Grade 4 • If toxicity improves to Grade ≤ 1 or baseline, resume study drug/study regimen after completion of steroid taper 	
For Grade 2 AST or ALT and or TB elevation :
 
 - Regular and frequent checking of LFTs (e.g. every 1-2 days) until elevations of these are improving or resolved. - If no resolution to \leq Grade 1 in 1-2 days, consider, as necessary, discussing with study physician. - If event is persistent (> 3-5 days) or worsens, promptly start prednisone 1-2mg/kg/day PO or IV equivalent. - If still no improvement within 3-5 days despite 1-2mg/kg/day of prednisone PO or IV equivalent, consider additional work up and start prompt treatment with IV methylprednisolone 2-4mg/kg/day. - If still no improvement within 3-5 days despite 2-4mg/kg/day of IV methylprednisolone, promptly start immunosuppressives (i.e., mycophenolate mofetil)⁶. Discuss with study physician if mycophenolate mofetil is not available. Infliximab should NOT be used. - Once the patient is improving, gradually taper steroids over ≥ 28 days and consider prophylactic antibiotics, antifungals and anti PJP treatment (please refer to current NCCN guidelines for

⁶ ASCO Educational Book 2015 “Managing Immune Checkpoint Blocking Antibody Side Effects”, by Michael Postow MD

	Grade of the Event (NCI CTCAE version 4.03)	Dose Modifications	Toxicity Management
			treatment of cancer-related infections [Category 2B recommendation])

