	Grade 3 (Based on ULN regardless of baseline LFT) (Grade 3: AST or ALT >5.0×ULN and ≤20.0×ULN and/or TB >3.0×ULN and ≤10.0×ULN)	
For elevations in transaminases ≤ 8 × ULN, or elevations in bilirubin ≤ 5 × ULN
 
 -Hold study drug/study regimen dose until resolution to ≤ Grade 1 or baseline -Resume study drug/study regimen if elevations downgrade ≤ Grade 1 or baseline within 14 days and after completion of steroid taper. 
Permanently discontinue study drug/study regimen if the elevations do not downgrade to ≤ Grade 1 or baseline within 14 days
 
For elevations in transaminases > 8 × ULN or elevations in bilirubin > 5 × ULN, discontinue study drug/study regimen
 
Permanently discontinue study drug/study regimen for any case meeting Hy's law criteria (AST and/or ALT > 3x ULN +
	
For Grade 3 or 4 AST or ALT and/or TB elevation:
 
 - Promptly initiate empiric IV methylprednisolone at 1 to 4 mg/kg/day or equivalent - If still no improvement within 3-5 days despite 1 to 4 mg/kg/day methylprednisolone IV or equivalent, promptly start treatment with immunosuppressive therapy (i.e., mycophenolate mofetil) 
Discuss with study physician if mycophenolate is not available. Infliximab should NOT be used.
 
 - Perform hepatology consult, abdominal workup, and imaging as appropriate. - Once the patient is improving, gradually taper steroids over ≥28 days and consider prophylactic antibiotics, antifungals and anti PJP treatment (please refer to current NCCN guidelines for treatment of cancer-related infections [Category 2B recommendation])

	Grade of the Event (NCI CTCAE version 4.03)	Dose Modifications	Toxicity Management

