
Hepatitis (elevated LFTs) Infliximab should not be used for management of immune-related hepatitis
 
THIS shaded area is guidance only for management of “Hepatitis (elevated LFTs)” in HCC.
 
See instructions at
	
Grade 4 (Grade 4: AST or ALT >20×ULN and/or TB >10×ULN)
 
Any Grade
	
bilirubin > 2x ULN without initial findings of cholestasis (i.e. elevated alkaline P04) and in the absence of any alternative cause⁷
 
Permanently discontinue study drug/study regimen
 
General Guidance
	
For any grade:
 
-Monitor and evaluate liver function test: AST, ALT, ALP, and TB.
 
-Evaluate for alternative etiologies (e.g., viral hepatitis, disease progression, concomitant medications, worsening of liver cirrhosis (e.g., portal vein thrombosis).)
 
-For HBV+ patients: evaluate quantitative HBV viral load, quantitative HBsAg, or HBcAg

⁷ FDA Liver Guidance Document 2009 Guidance for Industry: Drug Induced Liver Injury – Premarketing Clinical Evaluation

	Grade of the Event (NCI CTCAE version 4.03)	Dose Modifications	Toxicity Management

bottom of shaded area if transaminase rise is not isolated but (at any time) occurs in setting of either increasing bilirubin or signs of DILI/liver decompensation
	
Grade 1 (Isolated AST or ALT >ULN and $\leq 5.0 \times$ULN, whether normal or elevated at baseline)
	
 • No dose modifications. • If ALT/AST elevations represents significant worsening based on investigator assessment, then treat as Grade 2 event. 
For all grades, see instructions at bottom of shaded area if transaminase rise is not isolated but (at any time) occurs in setting of either increasing bilirubin or signs of DILI/liver decompensation
	
-For HCV+ patients: evaluate quantitative HCV viral load
 
-Consider consulting hepatologist/Infectious disease specialist regarding change/implementation in/of antiviral medications for any patient with an elevated HBV viral load >2000 IU/ml
 
-Consider consulting hepatologist/Infectious disease specialist regarding change/implementation in/of antiviral HCV medications if HCV viral load increased by >2 -fold
 
-For HCV+ with HBcAB+: Evaluate for both HBV and HCV as above

	Grade of the Event (NCI CTCAE version 4.03)	Dose Modifications	Toxicity Management

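### Section 6's hepatitis table gives conflicting hold-and-resume and stop instructions for some combined AST/ALT and bilirubin rises

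*Combined protocol and SAP*

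**What the plan says.** The table is in Section 6, Specific Immune-Mediated Reactions, Hepatitis (Elevated LFTs). All values below are multiples of ULN.

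- **Grade 2 row.** The range is "AST or ALT >3.0×ULN and $\leq 5.0 \times$ULN and/or TB >1.5×ULN and $\leq 3.0 \times$ULN". The instruction is "Hold Study drug/study regimen dose until grade 2 resolution to" Grade 1 or lower. On improvement to Grade 1 or lower or to baseline, the site is to "resume study drug/study regimen after completion of steroid taper". Hy's law is not mentioned.
- **Grade 3 row, hold clause.** Grade 3 is AST/ALT above 5 to 20 and/or bilirubin above 3 to 10. If transaminases are at most 8 *or* bilirubin is at most 5, dosing is held. It resumes if values downgrade within 14 days and the taper is complete; otherwise the stop is permanent.
- **Grade 3 row, discontinue clause.** "For elevations in transaminases > 8 × ULN or elevations in bilirubin > 5 × ULN, discontinue study drug/study regimen".
- **Grade 3 row, Hy's law sentence.** Permanent discontinuation for any case meeting Hy's "law criteria (AST and/or ALT > 3x ULN" plus "bilirubin > 2x ULN without initial findings of cholestasis", and with no alternative cause. The sentence runs over a page break but comes before the Grade 4 instruction, so it belongs to the Grade 3 cell.

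The shaded hepatitis block that follows is for HCC only and does not apply to NSCLC or colorectal patients.

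**The concern.** A site normally grades the event, finds the row and follows it. Here the most specific stopping sentence is printed one grade above the point at which its own cut-offs begin, and two clauses in the Grade 3 cell are not mutually exclusive. Two sites with identical laboratory results could follow different printed instructions, and each could point to the text.

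The choice has consequences. Under the additional information in Section 6, a hold also holds any remaining radiation, which resumes after the next drug dose. Permanent discontinuation for toxicity before treatment is complete takes the patient off treatment. Liver events are also a foreseeable question in this trial: Section 3.1.7 requires the irradiated lesion in the colorectal cohort to be in the liver, and Section 5.1 ranks liver first among organs for NSCLC irradiation.

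**Working it through.** The plan has no figure to reproduce. The check applies the printed cut-offs literally to pairs of values. Grade is the worse of the two tests. A test counts as an elevation only if it is above ULN. The Hy's law column uses only the two numeric cut-offs and assumes no initial cholestasis and no alternative cause.

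| AST/ALT, bilirubin | Grade | Hold then resume | Discontinue (8x/5x) | Hy's law stop |
|---|---|---|---|---|
| 4, 1.8 | 2 | yes | not in this row | no |
| 4, 2.5 | 2 | yes | not in this row | yes |
| 6, 2.5 | 3 | yes | no | yes |
| 10, 4 | 3 | yes (bilirubin) | yes (AST/ALT) | yes |
| 6, 6 | 3 | yes (AST/ALT) | yes (bilirubin) | yes |
| 10, 1.2 | 3 | yes (bilirubin) | yes (AST/ALT) | no |
| 10, 1.0 | 3 | no | yes | no |

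**Conflict 1, Hy's law sentence against hold and resume.** The Grade 2 bands are above 3 to 5 and above 1.5 to 3. Hy's law starts above 3 and above 2. They intersect at AST/ALT above 3 to 5 with bilirubin above 2 to 3. In Grade 3, the sentence also meets the hold clause, as at 6 and 2.5.

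**Conflict 2, the two Grade 3 clauses.** Hold applies at AST/ALT ≤ 8 or bilirubin ≤ 5; discontinue applies at AST/ALT > 8 or bilirubin > 5. With one elevated value on each side of its cut, both are true.

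**Extent of the overlap.** On a grid in steps of 0.1, with AST/ALT from 1.1 to 20 (190 values) and bilirubin from 1.1 to 10 (90 values):

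- Grade 2 points: 40 × 20 − 20 × 5 = 700. Of these, 20 × 10 = 200 also meet the Hy's law cut-offs.
- Grade 3 points: 190 × 90 − 40 × 20 = 16,300. Both clauses hold at 70 × 50 + 120 × 40 = 8,300.
- Of those 8,300, the number below a Hy's law cut-off is 20 × 50 + 120 × 10 = 2,200. The other 6,100 meet the numeric cut-offs.
- If a test may invoke a Grade 3 clause only when it is itself in the Grade 3 range, the overlap is 30 × 50 + 120 × 20 = 3,900. The pairs 10 and 4, and 6 and 6, are in this set.

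These counts show how far the rules overlap. They are not patient frequencies.

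**Source of conflict 2.** If the hold clause required both values to be at or below their cuts, its overlap with the discontinue clause would be zero, and conflict 1 would remain. This locates the cause and is not a proposed rule.

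**The case against.** The best defence is that a sentence covering any case is a specific override of the general hold-and-resume text, and that the worse test naturally governs in Grade 3. Section 6's general part also asks sites to consider permanent discontinuation for Grade 2 events with high likelihood of morbidity or mortality that do not improve rapidly, and the table is guidance that supports clinical judgement.

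Part of this stands. The override reading is plausible, especially within the Grade 3 cell, where a site sees both sentences. It does not settle the matter for Grade 2, because that row has no pointer. Where Section 6 wants a stop regardless of grade, it says so in an Any Grade row, as for myocarditis and bullous rash. The hepatitis Any Grade row contains only monitoring and work-up, and the general list of permanent-stop conditions omits Hy's law. The Grade 2 language in the general part is discretionary.

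It is also fair to say that 10x with 2.5x or 1.2x is a weak illustration of conflict 2, since bilirubin is then below Grade 3. The pairs 10x with 4x and 6x with 6x avoid this. Their values meet the Hy's law cut-offs, but the Hy's law sentence falls away if there is cholestasis or another cause, and the two clauses still collide.

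A reader might go further and infer that a Grade 2-level Hy's law case is left out of the dose-limiting toxicity (DLT) count and could decide whether an arm closes. The documents do not support that. Section 5.2 does list "Liver transaminase elevation $> 8 \times$ ULN or total bilirubin $> 5 \times$ ULN", so such a case is not automatically a DLT. But the same section lets an event below Grade 3 be declared one after consultation, and it has other routes for Grade 3 liver events. A permanent-stop criterion also need not coincide with a DLT.

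**Conclusion.** The contradiction is in the printed text, in two parts. For AST/ALT above 3 to 5x with bilirubin above 2 to 3x, the Grade 2 row and the Hy's law sentence give opposite outcomes once the patient has recovered; the same sentence also conflicts with the Grade 3 hold clause. The two Grade 3 clauses both apply whenever one elevated value is above its cut and the other is below.

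Conflict 1 arises only without initial cholestasis or an alternative cause. Liver metastases and liver radiation may often supply another cause in the colorectal cohort, so cases may be few. The planned 60 colorectal patients are an upper bound, since Section 13.4.1 stops an arm after ten patients without a response. It cannot be said that a Hy's law patient would in fact be re-dosed, only that the Grade 2 row read alone permits it. The point should be corrected for patient safety and consistency between sites. It does not bear on any endpoint, error rate or sample size, and which instruction is clinically right is not judged here.

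**What to change.** Reconcile the Grade 2 row, the two Grade 3 clauses and the Hy's law sentence so that each AST/ALT and bilirubin combination leads to one action. State the scope of the Hy's law sentence where a site reading any grade row will see it. Reword the two Grade 3 clauses so that they cannot both apply. The clinical team decides which action is intended in each case. Section 5.2 need not change for this point.

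The cost is a wording amendment to one table. No extra data are needed: AST, ALT, total bilirubin and alkaline phosphatase are already in the scheduled serum chemistry in Section 10.

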7. ADVERSE EVENTS: LIST AND REPORTING REQUIREMENTS

Adverse event (AE) monitoring and reporting is a routine part of every clinical trial. The following list of AEs (Section 7.1) and the characteristics of an observed AE (Section 7.2) will determine whether the event requires expedited reporting via the CTEP Adverse Event Reporting System (CTEP-AERS) **in addition** to routine reporting.

7.1 Comprehensive Adverse Events and Potential Risks List(s) (CAEPRs)

The Comprehensive Adverse Event and Potential Risks list (CAEPR) provides a single list of reported and/or potential adverse events (AE) associated with an agent using a uniform presentation of events by body system. In addition to the comprehensive list, a subset of AEs, the Specific Protocol Exceptions to Expedited Reporting (SPEER), appears in a separate column and is identified with **bold** and *italicized* text. The SPEER is a list of events that are protocol-specific exceptions to expedited reporting to NCI (except as noted below). Refer to the 'CTEP, NCI Guidelines: Adverse Event Reporting Requirements' http://ctep.cancer.gov/protocolDevelopment/adverse_effects.htm for further clarification.

NOTE: The highest grade currently reported is noted in parentheses next to the AE in the SPEER. Report **ONLY** AEs higher than this grade expeditiously. If this CAEPR is part of a combination protocol using multiple investigational agents and has an AE listed on different SPEERs, use the lower of the grades to determine if expedited reporting is required.

7.1.1 CAEPRs for CTEP IND Agent(s)

7.1.1.1 CAEPR for MEDI4736

Comprehensive Adverse Events and Potential Risks list (CAEPR) for MEDI4736 (durvalumab, NSC 778709)

The Comprehensive Adverse Events and Potential Risks list (CAEPR) provides a single list of reported and/or potential adverse events (AE) associated with an agent using a uniform presentation of events by body system. In addition to the comprehensive list, a subset, the Specific Protocol Exceptions to Expedited Reporting (SPEER), appears in a separate column and is identified with bold and italicized text. This subset of AEs (SPEER) is a list of events that are protocol specific exceptions to expedited reporting to NCI (except as noted below). Refer to the 'CTEP, NCI Guidelines: Adverse Event Reporting Requirements' http://ctep.cancer.gov/protocolDevelopment/electronic_applications/docs/aeguidelines.pdf for further clarification. *Frequency is provided based on 2833 patients.* Below is the CAEPR for MEDI4736 (durvalumab).

NOTE: Report AEs on the SPEER **ONLY IF** they exceed the grade noted in parentheses next to the AE in the SPEER. If this CAEPR is part of a combination protocol using multiple investigational agents and has an AE listed on different SPEERs, use the lower of the grades to determine if expedited reporting is required.

April 17, 2019¹

Adverse Events with Possible Relationship to MEDI4736 (durvalumab) (CTCAE 5.0 Term) [n= 2833]			Specific Protocol Exceptions to Expedited Reporting (SPEER)
Likely (>20%)	Less Likely (<=20%)	Rare but Serious (<3%)	
BLOOD AND LYMPHATIC SYSTEM DISORDERS			
		Blood and lymphatic system disorders - Other (idiopathic thrombocytopenic purpura) ²	
		Thrombotic thrombocytopenic purpura ²	
CARDIAC DISORDERS			
		Myocarditis ²	
		Pericarditis ²	
ENDOCRINE DISORDERS			
		Adrenal insufficiency ²	
		Endocrine disorders - Other (diabetes insipidus)	
		Endocrine disorders - Other (diabetes mellitus type 1) ²	
	Hyperthyroidism ²		
		Hypopituitarism ²	
	Hypothyroidism ²		
EYE DISORDERS			
		Keratitis ²	
		Uveitis ²	
GASTROINTESTINAL DISORDERS			
	Abdominal pain		Abdominal pain (Gr 2)
		Colitis ²	
	Diarrhea		Diarrhea (Gr 2)
		Gastrointestinal disorders - Other - (gastrointestinal perforation) ^{2,3}	
	Nausea		Nausea (Gr 2)
		Pancreatitis ²	
	Vomiting		Vomiting (Gr 2)
GENERAL DISORDERS AND ADMINISTRATION SITE CONDITIONS			
	Edema limbs		Edema limbs (Gr 2)
	Fatigue		Fatigue (Gr 2)
	Fever		Fever (Gr 2)
HEPATOBIILIARY DISORDERS			
		Hepatobiliary disorders - Other (autoimmune hepatitis) ²	
IMMUNE SYSTEM DISORDERS			
		Immune system disorders - Other (immune related adverse events) ²	
		Immune system disorders - Other (sarcoidosis)	
INFECTIONS AND INFESTATIONS			
	Infection ⁴		Infection⁴ (Gr 2)
INJURY, POISONING AND PROCEDURAL COMPLICATIONS			

Adverse Events with Possible Relationship to MEDI4736 (durvalumab) (CTCAE 5.0 Term) [n= 2833]			Specific Protocol Exceptions to Expedited Reporting (SPEER)
Likely (>20%)	Less Likely (<=20%)	Rare but Serious (<3%)	
		Infusion related reaction	
INVESTIGATIONS			
	Alanine aminotransferase increased ²		Alanine aminotransferase increased² (Gr 2)
	Aspartate aminotransferase increased ²		Aspartate aminotransferase increased² (Gr 2)
	Creatinine increased		Creatinine increased (Gr 2)
METABOLISM AND NUTRITION DISORDERS			
	Anorexia		Anorexia (Gr 2)
MUSCULOSKELETAL AND CONNECTIVE TISSUE DISORDERS			
	Arthritis ²		
		Musculoskeletal and connective tissue disorder - Other (polymyositis) ²	
	Myalgia		Myalgia (Gr 2)
		Myositis ²	
NERVOUS SYSTEM DISORDERS			
		Guillain-Barre syndrome ^{2,5}	
		Myasthenia gravis ²	
		Nervous system disorders - Other (aseptic meningitis) ²	
		Peripheral sensory neuropathy	
RENAL AND URINARY DISORDERS			
	Dysuria		Dysuria (Gr 2)
		Renal and urinary disorders - Other (autoimmune nephritis) ²	
RESPIRATORY, THORACIC AND MEDIASTINAL DISORDERS			
Cough			Cough (Gr 2)
	Dyspnea		Dyspnea (Gr 2)
	Pneumonitis ²		
	Respiratory, thoracic and mediastinal disorders - Other (dysphonia)		
SKIN AND SUBCUTANEOUS TISSUE DISORDERS			
	Hyperhidrosis		
	Pruritus		Pruritus (Gr 2)
	Rash ^{2,6}		Rash^{2,6} (Gr 2)
		Skin and subcutaneous tissue disorders - Other (scleroderma)	
		Skin and subcutaneous tissue disorders - Other (severe dermatitis) ^{2,7}	
	Skin hypopigmentation		Skin hypopigmentation (Gr 2)

NOTE: Cardiomyopathy, and graft versus host disease, while not observed on clinical trials of MEDI4736 (durvalumab) at this time, are known events with this class of agent (PD-L1 antagonist).

¹This table will be updated as the toxicity profile of the agent is revised. Updates will be distributed to all Principal Investigators at the time of revision. The current version can be obtained by contacting [contact]. Your name, the name of the investigator, the protocol and the agent should be included in the e-mail.

²Immune-mediated adverse reactions (irAEs) have been reported in patients receiving MEDI4736 (durvalumab). irAEs can involve any of the organs or systems in the body. Most irAEs were reversible and managed with interruptions of MEDI4736 (durvalumab), administration of corticosteroids and supportive care, however, these events can be serious and fatal.

³Gastrointestinal perforations have been observed only in patients receiving MEDI4736 (durvalumab) in combination with tremelimumab (CP-675,206).

⁴Infections includes infection in the lungs, upper respiratory tract, dental and oral soft tissues and other organs under the INFECTIONS AND INFESTATIONS SOC. Infections generally are mild (Gr 1-2) but severe infections including sepsis, necrotizing fasciitis, and osteomyelitis have been reported.

⁵Guillain-Barre Syndrome has been reported in patients receiving MEDI4736 (durvalumab) in combination with tremelimumab (CP-675,206) but can potentially occur after durvalumab monotherapy.

⁶Rash includes the terms: rash erythematous, rash generalized, rash macular, rash maculopapular, rash papular, rash pruritic, rash pustular, erythema, and eczema.

⁷In rare cases, severe dermatitis has been reported to manifest as Stevens-Johnson syndrome, toxic epidermal necrolysis, or rashes complicated by dermal ulceration or necrotic, bullous, or hemorrhagic manifestations.

Adverse events reported on MEDI4736 (durvalumab) trials, but for which there is insufficient evidence to suggest that there was a reasonable possibility that MEDI4736 (durvalumab) caused the adverse event:

BLOOD AND LYMPHATIC SYSTEM DISORDERS - Anemia; Disseminated intravascular coagulation

CARDIAC DISORDERS - Atrial fibrillation; Atrial flutter; Cardiac disorders - Other (coronary artery disease); Pericardial effusion; Pericardial tamponade; Restrictive cardiomyopathy; Right ventricular dysfunction; Sinus tachycardia

EAR AND LABYRINTH DISORDERS - Hearing impaired

EYE DISORDERS - Eye disorders - Other (choroidal effusion with shut down of ciliary body)

GASTROINTESTINAL DISORDERS - Ascites; Constipation; Dental caries; Gastrointestinal disorders - Other (gastrointestinal hemorrhage); Mucositis oral; Proctitis; Small intestinal obstruction; Upper gastrointestinal hemorrhage

GENERAL DISORDERS AND ADMINISTRATION SITE CONDITIONS - Edema trunk; Non-cardiac chest pain; Pain

HEPATOBIILIARY DISORDERS - Hepatic hemorrhage

IMMUNE SYSTEM DISORDERS - Immune system disorders - Other (drug-induced liver injury); Serum sickness

INJURY, POISONING AND PROCEDURAL COMPLICATIONS - Wound complication

INVESTIGATIONS - Blood bilirubin increased; CPK increased; Electrocardiogram T wave abnormal; GGT increased; Lipase increased; Lymphocyte count decreased; Neutrophil count decreased; Platelet count decreased; Serum amylase increased; Weight loss; White blood cell decreased

METABOLISM AND NUTRITION DISORDERS - Dehydration; Hypercalcemia; Hyperglycemia; Hyperkalemia; Hypermagnesemia; Hypoalbuminemia; Hypokalemia; Hypomagnesemia; Hyponatremia

MUSCULOSKELETAL AND CONNECTIVE TISSUE DISORDERS - Arthralgia; Back pain; Rhabdomyolysis

NEOPLASMS BENIGN, MALIGNANT AND UNSPECIFIED (INCL CYSTS AND POLYPS) - Neoplasms benign, malignant and unspecified (incl cysts and polyps) - Other (brain metastasis swelling); Neoplasms

benign, malignant and unspecified (incl cysts and polyps) - Other (lung cyst); Neoplasms benign, malignant and unspecified (incl cysts and polyps) - Other (tumor flare, tumor inflammation); Treatment related secondary malignancy; Tumor hemorrhage; Tumor pain

NERVOUS SYSTEM DISORDERS - Ataxia; Dizziness; Edema cerebral; Headache; Nervous system disorders - Other (axonal neuropathy); Nervous system disorders - Other (hemiparesis); Paresthesia; Seizure

PSYCHIATRIC DISORDERS - Confusion

RENAL AND URINARY DISORDERS - Acute kidney injury

RESPIRATORY, THORACIC AND MEDIASTINAL DISORDERS - Bronchopulmonary hemorrhage; Hypoxia; Pleural effusion; Pneumothorax; Respiratory failure

SKIN AND SUBCUTANEOUS TISSUE DISORDERS - Bullous dermatitis; Dry skin

VASCULAR DISORDERS - Hypertension

Note: MEDI4736 (durvalumab) in combination with other agents could cause an exacerbation of any adverse event currently known to be caused by the other agent, or the combination may result in events never previously associated with either agent.

